13.4. Other statistical considerations

- 13.4.1. The impact of ⁶⁸Ga PSMA-HBED-CC PET/CT on clinical management in BCR patients will be evaluated using descriptive statistics.
- 13.4.2. Inter-reader reproducibility for positivity at the patient level and region level will be reported using the Fleiss' Kappa test for multiple readers.
- 13.4.3. Safety will be reported descriptively as rates of patient reported adverse events.

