1.2. Secondary objective

- 1.2.1. Determine positive predictive value on a per-subject and per-region basis of ^{68}Ga PSMA-HBED-CC PET/CT for detecting tumor location, confirming with histopathology and conventional imaging.
- 1.2.2. Continue to evaluate safety of ^{68}Ga PSMA-HBED-CC injection as categorized by CTCAE 4.03.

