6.2. Pre-Imaging Assessments (Baselines)

- 6.2.1. **Constitutional adverse events.** A baseline evaluation will be obtained prior to injection and will be graded against CTCAE.
- 6.2.2. **Vital signs.** Heart rate, blood pressure, and temperature will be obtained immediately before and after injection of ⁶⁸Ga PSMA-HBED-CC, in a supine position.

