6.3. Post-Imaging Assessments

- 6.3.1. **Vital signs.** Heart rate, blood pressure, and temperature will be obtained when subject is supine immediately after the imaging.
- 6.3.2. **Constitutional adverse events.** Prior to discharge from the PET Imaging Center, the subject will be assessed for untoward medical event(s) that have occurred since injection of ⁶⁸Ga PSMA-HBED-CC. These will be graded with CTCAE.
- 6.3.3. **Symptom review.** Subject will be contacted by telephone or in person between 1 to 3 business days after PSMA-HBED-CC imaging to screen for

adverse events. Subject must be contacted at least once after 24h post-injection.

6.4. **Follow-up**

- 6.4.1. **Change in management.** A post-imaging survey of clinical management using PSMA-HBED-CC PET/CT information will be performed \leq 30 days of PSMA-HBED-CC PET/CT imaging for assessment of change in clinical management.
- 6.4.2. **Change in management 6 months post imaging.** A survey of clinical management will be performed approximately 6 month after the PSMA-HBED-CC PET/CT imaging for assessment of change in clinical management.
- 6.4.3. **Follow-up imaging.** Conventional imaging ordered per standard of care up to 12 months post ^{68}Ga PSMA-HBED-CC PET/CT, will be obtained for study analysis. If imaging is NOT obtained per standard of care the research study will obtain a CT (abdomen and pelvis w/ contrast if contrast not contraindicated). Readers will be unblinded to all results and will be specifically informed of the location of the ^{68}Ga PSMA-HBED-CC PET positive lesions so follow-up measurements may be performed on the same lesions.
- 6.4.4. **Pathology.** Results from pathology ordered per standard of care up to 12 months post ^{68}Ga PSMA-HBED-CC PET/CT, will be obtained for study analysis.
- 6.4.5. **Laboratory.** Results from laboratory reports related to prostate cancer monitoring (e.g. PSA levels) ordered per standard of care up to 12 months post ^{68}Ga PSMA-HBED-CC PET/CT, will be obtained for study analysis.
- 6.4.6. **Second ^{68}Ga PSMA-HBED-CC PET/CT (if medically indicated).** If the 1st ^{68}Ga PSMA-HBED-CC PET/CT scan shows lymph nodes or visceral (soft tissue) lesions positive for prostate cancer disease, but surgery or biopsy results in negative pathology; the subject may be asked to return to complete a 2nd ^{68}Ga PSMA-HBED-CC PET/CT imaging visit.

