Secondary: PPVs on a per-subject and per-region-basis of ^{68}Ga PSMA-HBED-CC for detection of tumor location confirmed by histopathology/biopsy and conventional imaging follow-up will be calculated and reported along with the corresponding two-sided 95% confidence intervals. The confidence intervals will be constructed using the Wilson score method.

The following definitions will define accuracy of ^{68}Ga PSMA-HBED-CC for detection of tumor location confirmed by histopathology/biopsy and conventional imaging follow-up

No statistical significance will be generated due to the pilot nature of the project.

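### Section 13.4.3 reports only patient-reported adverse events, which is narrower than the CTCAE-based safety objective and the safety data the protocol collects

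*Combined protocol and SAP*

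**What the plan says.** - **Objective.** Section 1.2.2 sets, as a secondary objective, continued evaluation of the safety of the tracer "injection as categorized by CTCAE 4.03".
- **Analysis.** Section 13.4.3 is the only statement of how safety will be analysed: "Safety will be reported descriptively as rates of patient reported adverse events". It mentions no grade, staff-observed events, vital signs or denominator.
- **Other secondary endpoints.** The secondary paragraph of 13.2 covers "PPVs on a per-subject and per-region-basis of" the tracer and nothing on safety.
- **Collection before the scan.** Section 6.2.1: "A baseline evaluation will be obtained prior to injection and will be graded against CTCAE". Section 6.2.2: "Heart rate, blood pressure, and temperature will be obtained immediately before and after injection of" the tracer.
- **Collection after the scan.** Section 6.3.1: "Heart rate, blood pressure, and temperature will be obtained when subject is supine immediately after the imaging". Section 6.3.2 adds that before discharge "the subject will be assessed for untoward medical event(s) that have occurred since injection of" the tracer, and "These will be graded with CTCAE". Section 6.3.3 adds a symptom contact 1 to 3 business days later.
- **Adverse event rules.** Section 9.1 has the research team bring every toxicity and adverse event to the principal investigator. It requires CTCAE v4 grading, with attribution for Grade 3 and above and for all serious events. Sections 9.4 and 9.5 send the routine log and serious-event notices to the DSMC.

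**The concern.** An analysis sentence normally takes in at least what its objective names. Here the objective speaks of CTCAE categories and the procedures generate staff-assessed, graded data, but the analysis sentence selects events by who reported them. The adverse events most likely to fall outside a patient-reported count are those a subject does not feel, and the vital-sign measurements around injection and after imaging are the protocol's means of finding them.

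At stake is the completeness of the safety result for a secondary objective. The rationale in 2.5 says the data are meant to support further approvals of the compound. A rate built on a narrower definition than the objective's would be harder to defend there, and harder to pool with other sites' results, which 13.1 contemplates for sensitivity.

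**Working it through.** The plan states no safety figure to reproduce, so the check is a comparison of text followed by one piece of arithmetic for scale.

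**1. Objective against analysis.** The objective (1.2.2) classifies events by CTCAE. The analysis (13.4.3) selects events by source, the patient, and does not mention CTCAE. The two differ in scope and in form of summary.

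**2. Collection against analysis.**

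| Collected item | Section | Depends on the subject reporting it? | Inside 13.4.3 as worded? |
|---|---|---|---|
| Graded baseline evaluation | 6.2.1 | Partly | Use not stated |
| Vital signs before and after injection | 6.2.2 | No | No |
| Vital signs after imaging | 6.3.1 | No | No |
| Graded assessment before discharge | 6.3.2 | Partly | Only what the subject reports |
| Symptom contact | 6.3.3 | Yes | Yes |
| All toxicities and adverse events, graded | 9.1 | No | Only what the subject reports |

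**3. Does another statement fill the gap?** Section 13.2 deals with sensitivity and positive predictive value. Sections 9.2 to 9.5 govern reporting to the IRB, the FDA and the DSMC. These are oversight routes and none defines a study result. Section 13.4.3 therefore stands alone.

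**4. One event followed through.** Take a vital-sign change without symptoms that qualifies as an adverse event.
- It is measured under 6.2.2 or 6.3.1.
- It is graded and passed to the principal investigator under 6.3.2 and 9.1.
- It goes to the DSMC on the log (9.4), or by notice if serious (9.5).
- At 13.4.3 it is not a patient-reported event, so it does not enter the rate.

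**5. Scale.** The planned sample is 30 (13.1). If k subjects have only staff-observed events, the proportion of subjects with any event is understated by k/30:
- k = 0: 0 points
- k = 1: 1/30 = 3.3 points
- k = 2: 2/30 = 6.7 points
- k = 3: 3/30 = 10.0 points

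The values of k are assumptions. The documents give no expected number of such events, so this shows how coarse the rate is and not how wrong it will be.

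**The case against.** The strongest reply is that the phrase in 13.4.3 is loose wording for all events recorded in patients. Section 9.1 already requires every adverse event to be identified, 6.3.2 covers any untoward event, and the protocol defines no separate patient-reported dataset. The sentence does not contain the word "only". That reading is possible, but nothing in the documents confirms it, and an analyst following the sentence as written would exclude staff-observed events. The study is also a descriptive pilot, and 2.4 cites more than 1200 subjects in the literature without noted adverse reactions, so few events may be affected. That limits the importance of the point without removing it.

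Several stronger readings are tempting, and the documents do not support them:
- **Baseline symptoms will be counted as events.** Section 6.3.2 confines the discharge assessment to events since injection, and 9.4 starts documentation of non-serious events at injection. What is missing is only a rule for a baseline condition that worsens.
- **CTCAE grading is absent, or the objective cannot be met.** Grading is fixed in 1.2.2, 6.2.1, 6.3.2 and 9.1. It is simply not carried into 13.4.3, and the objective can be met from the data already planned.
- **Staff-observed events are lost.** They are recorded and reach the DSMC. They are missing from the reported rate, not from the trial.
- **A table of vital-sign changes is owed.** No objective or endpoint asks for one.

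**Conclusion.** The point holds as a mismatch between a stated analysis rule and the trial's own objective and data collection. Read as written, 13.4.3 leaves adverse events noticed by staff, but not reported by the subject, out of the safety rate, and no other statement brings them back. It is a fault in the analysis wording and not in data collection.

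The conclusion rests on two assumptions: that 13.4.3 is applied literally, and that at least some qualifying events would be staff-observed only. If no such event occurs, the overall rate is unchanged, although 13.4.3 would still not present it by grade as 1.2.2 implies. The size cannot be quantified from the documents. The matter is minor for the trial as a whole, and worth correcting because the correction is easy.

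**What to change.** Replace 13.4.3 with wording to this effect: safety will be summarised descriptively as the number and percentage of injected subjects with any adverse event recorded after injection, whether reported by the subject or observed by staff (including vital-sign changes that meet CTCAE criteria), by highest CTCAE grade per subject. A condition present at baseline counts only if it worsens from its pre-injection grade.

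Two small clarifications belong in the same edit. Name one CTCAE version throughout (1.2.2 says 4.03, 9.1 says v4), and state how events after a second injection under 6.4.6 are counted. A descriptive summary of the collected vital signs at each time point is an optional addition.

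The cost is a short text change and a simple table, or two if vital signs are added. All the data are already planned for collection, and the sample size, error rates and other endpoints are unaffected.
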